7.1.2 Selection of Data for LTE Baseline

The LTE baseline value will be chosen based on the rules specified below, unless otherwise specified. Note that LTE Baseline is applicable only to Group P-TC, unless otherwise specified.

7.1.2.1 Measurements Without a Source Recording Measurement Time Point

The baseline value will be the last non-missing and evaluable value prior to or on LTE Study Day 1.

If multiple non-missing and evaluable records occur on the same day that is closest to LTE Study Day 1 or on LTE Study Day 1:

- For continuous measurements other than laboratory and PD biomarker data, the best of these records will be considered the baseline value.
- For continuous measurements for laboratory and PD biomarker data, the average of these records will be considered the baseline value.
- For categorical measurements regardless the type of endpoints (not applicable to categorical measurements derived from continuous measurements), the record with the lowest severity will be considered the baseline value, for example:
 - Lower grade severity will be selected over higher grade severity for toxicity grades or severity;
 - “normal” will be selected over “low” and “high” for a test or exam with those categories;
 - “normal” will be selected over “abnormal” for a test or exam with those two categories;
 - “negative” will be selected over “positive” for a test or exam with those two categories.

7.1.2.2 Measurements With a Source Recording Measurement Time Point

For measurements that have a source recording the measurement time point (e.g., the measurement time point of vital signs and ECG data are recorded on the corresponding electronic CRF; the measurement time point of sTREM2 data is recorded in the vendor data), the baseline value will be the last non-missing and evaluable value prior to LTE Study Day 1, or the last non-missing and evaluable value with “predose” missing, or “not applicable” (i.e., excluding value collected post infusion) as the measurement time point (as recorded in the source data) on LTE Study Day 1. Non-missing values with “post infusion” (or containing “end of infusion” (EOI)) as the measurement time point (as recorded in the source data) on Study Day 1 are not considered candidates for the baseline value and will be assigned the analysis visit “Day 1 Postdose” (^a Target Day and Core Study Day are based on Core Study Day 1.

^b LTE Day 1 represents Core Study Day of first dose date of LTE Study. If no such date, use Core study day of the last visit date among Core visits and LTE screening visit.

Table 7-6. Analysis Visit Windows for Coagulation Assessments Based on LTE Study Day^a

| Analysis Visit | Target Day | Analysis Visit Window |
|-----------------------|-------------------|------------------------------|
| LTE Baseline | 1 | ≤ 1 |
| LTE Week 56 | 393 | > 1 |

^a Target Day and LTE Study Day are based on LTE Study Day 1.

Table 7-7 and ^a Target Day and Core Study Day are based on Core Study Day 1.

^b LTE Day 1 represents Core Study Day of first dose date of LTE Study. If no such date, use Core study day of the last visit date among Core visits and LTE screening visit.

Table 7-10) when applicable.

If multiple non-missing and evaluable records occur on the same day that is closest to LTE Study Day 1 (not on LTE Study Day 1), or on LTE Study Day 1 and all with “predose”, missing, or “not applicable” as the measurement time point:

- For continuous measurements, the average of these values will be considered the baseline value.
- For categorical measurements (not applicable to categorical measurements derived from continuous measurements), the record with the lowest severity will be considered the baseline value (e.g., “abnormal not clinically significant” will be selected over “abnormal clinically significant”).

7.1.3 Selection of Data in the Event of Multiple Records in a Post-Baseline Analysis Visit Window

7.1.3.1 Efficacy Data

For non-composite efficacy endpoints:

If multiple valid, non-missing efficacy records exist in a post-baseline analysis visit window, records will be chosen based on the following rules if a single value is needed, unless otherwise specified:

- The record closest to the target day (in terms of days) for that visit will be selected.
- If there are multiple records that are equidistant from the target day (in terms of days), the later record will be selected.
- If there are multiple records on the same day and the chronological order (in terms of day and time) can be determined (e.g., with time known on the same day), the latest record will be selected.
- If there are multiple records on the same day and the chronological order cannot be determined (e.g., more than one record on the same day with time missing), the worst record will be selected.

For composite efficacy endpoints (ADCOMS and modified iADRS):

Refer to Section 6.4.2.5 and 6.4.2.6 for scenarios when components of composite endpoints are from different day.

If all the individual components have no multiple records on the same day, then the composite score is first calculated based on all the individual components collected on the same day. After the composite score is calculated, if multiple composite scores exist in a post-baseline analysis visit window, then:

- The record closest to the target day (in terms of days) for that visit will be selected.
- If there are multiple records that are equidistant from the target day (in terms of days), the later record will be selected.

If one or more individual components have multiple records on the same day, then the following rules of selection for those individual components apply first, followed by the rules above to calculate and select the composite score:

- If there are multiple records on the same day and the chronological order (in terms of day and time) can be determined (e.g., more than one record with time known on the same day), the latest record will be selected.
- If there are multiple records on the same day and the chronological order cannot be determined (e.g., more than one record on the same day with time missing), the worst record will be selected.

7.1.3.2 Safety and PD Biomarker Data

Depending on the statistical analysis method, a single value may be required for each analysis visit window (e.g., CFB by visit usually requires a single value), except for “>90 Days Post Last Dose” analysis visit window.

For safety data, if multiple valid, non-missing, continuous records exist in a post-baseline analysis visit window, records will be chosen based on the following rules if a single value is needed, unless otherwise specified:

- The record closest to the target day (in terms of days) for that visit will be selected.
- If there are multiple records that are equidistant from the target day (in terms of days), the later record will be selected.
- If there are multiple records on the same day (regardless of time), the average will be taken.

For exploratory PD biomarker data, if multiple valid, non-missing, continuous records exist in a post-baseline analysis visit window, then the average of these records will be taken.

For safety and exploratory PD biomarker data, if multiple valid, non-missing, categorical records exist in a post-baseline analysis visit window (not applicable to categorical measurements derived from continuous measurements), records will be chosen based on the following rules if a single value is needed, unless otherwise specified:

- The record closest to the target day for that visit (in terms of days) will be selected.
- If there are multiple records that are equidistant from the target day (in terms of days), the later record will be selected.
- If there are multiple records on the same day, the record with the worst severity will be selected, for example:
 - higher grade severity will be selected over lower grade severity for toxicity grades;
 - “low” or “high” will be selected over “normal” for a test or exam with those categories;
 - “abnormal” will be selected over “normal” for a test or exam with those two categories;
 - “positive” will be selected over “negative” for a test or exam with those two categories.

For those categorical measurements derived from continuous measurements, if multiple valid, non-missing, continuous records exist in an analysis visit window, the rules for selecting a single value for continuous measurements apply first, then the corresponding categorical measurements will be derived based on the single selected continuous measurements.

Measurements that are collected both predose and post-infusion also follow the above rules for post-baseline visits, but per each measurement time point (i.e., per predose, per post-infusion, and not applicable).

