**Description of Study Periods and Visits:**

*Screening/Baseline Period: Prior to AL002-LTE Study Entry (from Day -28 to Day -1)*

As described in the sections above, the participant and/or their study partner may sign the informed consent/assent for AL002-LTE during the final dosing visit of the parent study. This will mark the beginning of the screening/baseline period for AL002-LTE. Required safety and/or eligibility assessments may be obtained at any time prior to dosing on Day 1/Week 1. The screening/baseline period may also be utilized to obtain any efficacy assessments (eg, COAs) that were not collected from the parent study in the last 12 weeks prior to Day1/Week 1. For those participating in the amyloid or Tau PET sub-studies in the AL002-2 trial, a new longitudinal amyloid and Tau PET imaging will be required if the last timepoint from the parent study was taken more than 24 weeks prior to Day 1/Week 1. Baseline MRIs are required if the last MRI occurred more than 90 days prior to the first dose on Day 1/Week 1 of AL002-LTE. For those participating in optional CSF sampling, an optional LP will need to be collected prior to Day 1/Week 1 if it has been more than 12 weeks since the last evaluation. The C-SSRS must be completed during the screening/baseline period.

Once eligibility is confirmed and the appropriate safety assessments have been collected, enrollment can occur any time after signing the informed consent and prior to the AL002-LTE first dose on Day 1/Week 1.

Participants will be offered the opportunity to consent for the optional exploratory biomarker assessments (CSF sampling, longitudinal Amyloid PET and Tau PET) even if they did not previously agree in the parent study. Details for the optional PET imaging assessments including objectives, eligibility criteria, sample collection, and imaging specifications are provided in the PET Imaging Procedures Manual. Consent for the optional assessments will be documented. Participation in the optional PET imaging procedures will be allowed according to local country regulations. The screening/baseline period can be utilized to capture the initial timepoint, which will serve as the participant's baseline and will not be used to determine eligibility.

*Treatment Period (Day 1/Week 1 to Week 49)*

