- g. Perform/collect prior to dosing. For all post-screening MRIs, the MRI should occur at least 5 days prior to the next dose administration and no more than 10 days prior to the next dose administration, with results received from the central imaging vendor prior to dosing. Note that the central imaging vendor typically requires 5 business days after receipt of the MRI before sending a BMW to the site. MRIs may be scheduled outside of the prescribed window, with approval from the Medical Monitor. The Sponsor may request that additional unscheduled MRIs be performed for the detection and follow-up of ARIA. Participants with MRI evidence of ARIA should be managed according to instructions provided in [Table 8](#).
- h. Vital signs include temperature, respiratory rate, pulse rate, and systolic and diastolic BP while the participant is at rest in a supine position for at least 3 minutes. Heart rate and BP measurements should be obtained with a validated digital monitoring device where available and an appropriately sized cuff. The same arm should be used for all BP measurements if possible. Heart rate and BP should not be measured unless 15 minutes have passed since the last blood draw.
- i. Perform/collect prior to dosing, and at the end of the infusion. Vital signs will be collected and concomitant medications and AEs documented prior to and at the end of infusion. On dosing visits, serum PK samples will be collected pre-dose. On non-dosing visits, serum PK samples may be collected at any time during the visit. Blood samples for assessment of ADA will be taken throughout the study.
- j. Urine pregnancy test (WOCBP only) and vital signs will be performed, and concomitant medications and AEs will start being collected at the screening/baseline visit and subsequent visits for those participants participating in a Tau PET scan.
- k. Complete PE includes evaluation of the head, eyes, ears, nose, and throat, and the cardiovascular, dermatological, musculoskeletal, respiratory, and gastrointestinal systems. Breast, rectal, and genitourinary exams should be performed as clinically indicated. Limited exams should include cardiovascular, respiratory, and gastrointestinal systems. Symptom-directed PEs may also include any other pertinent system as required.
- l. Neurological examination includes an evaluation of consciousness, orientation, cranial nerves, motor and sensory system, coordination and gait, and reflexes.

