Table 7-12. Analysis Visit Windows for MRI Assessments Based on Core Study Day ^a

| Analysis Visit | Target Day | T-T Analysis Visit Window | P-TC Analysis Visit Window ^b |
|----------------|------------|---------------------------|---|
| Core Baseline | - | ≤ 1 | ≤ 1 |
| Week 2 | 15 | [2, 22] | [2, 22] |
| Week 4 | 29 | [23, 36] | [23, 36] |
| Week 6 | 43 | [37, 50] | [37, 50] |
| Week 8 | 57 | [51, 71] | [51, 71] |
| Week 12 | 85 | [72, 127] | [72, 127] |
| Week 24 | 169 | [128, 253] | [128, 253] |
| Week 48 | 337 | [254, 421] | [254, min (421, LTE Day 1)] |
| Week 72 | 505 | [422, 589] | [422, min (589, LTE Day 1)] |
| Week 96 | 673 | [590, 715] | [590, LTE Day 1] |
| Week 108 | 757 | [716, 785] | LTE Week 8 ^c |
| Week 116 | 813 | [786, 841] | LTE Week 16 ^c |
| Week 124 | 869 | [842, 897] | LTE Week 24 ^c |
| Week 132 | 925 | [898, 953] | LTE Week 32 ^c |
| Week 140 | 981 | [954, 1037] | LTE Week 40 ^c |
| Week 156 | 1093 | > 1037 | LTE Week 56 ^c |

^a Target Day and Core Study Day are based on Core Study Day 1.

^b LTE Day 1 represents Core Study Day of first dose date of LTE Study. If no such date, use Core study day of the last visit date among Core visits and LTE screening visit.

^c LTE Weeks are from [Table 7-13](#). Mapping done only for volumetric MRI assessments, not for ARIA event results.

Table 7-13. Analysis Visit Windows for MRI Assessments Based on LTE Study Day ^a

| Analysis Visit | Target Day | Analysis Visit Window |
|----------------|------------|-----------------------|
| LTE Baseline | 1 | ≤ 1 |
| LTE Week 8 | 57 | [2, 85] |
| LTE Week 16 | 113 | [86, 141] |
| LTE Week 24 | 169 | [142, 197] |
| LTE Week 32 | 225 | [198, 253] |
| LTE Week 40 | 281 | [254, 337] |
| LTE Week 56 | 393 | > 337 |

^a Target Day and LTE Study Day are based on LTE Study Day 1.

Table 7-14. Analysis Visit Windows for Ophthalmological Examination Based on Core Study Day ^a

| Analysis Visit | Target Day | T-T Analysis Visit Window | Placebo Analysis Visit Window ^b |
|----------------|------------|---------------------------|--|
| Core Baseline | - | ≤ 1 | ≤ 1 |
| Week 6 | 43 | [2, 78] | [2, 78] |
| Week 16 | 113 | [79, 169] | [79, 169] |
| Week 32 | 225 | [170, 281] | [170, 281] |
| Week 48 | 337 | [282, 421] | [282, min (421, LTE Day 1)] |
| Week 72 | 505 | [422, 589] | [422, min (589, LTE Day 1)] |
| Week 96 | 673 | [590, 687] | [590, min (687, LTE Day 1)] |
| Week 100 | 701 | [688, 757] | [688, LTE Day 1] |
| Week 116 | 813 | [758, 869] | |

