7.7.3 Pharmacodynamic (PD) Assessment of Biomarker Endpoints

For Integrated Analysis, similar analyses listed in section 7.6.2 for efficacy endpoints will be provided for biomarker endpoints. Specifically, for CSF and plasma biomarkers, volumetric MRI, amyloid PET and Tau PET parameters [Table 7-39], the analyses will be based on the integrated data up to Week 96 since the initiation of study treatment from both the Core Study and the LTE study for the treatment groups and the data from the Core Study and the LTE screening data for the placebo treatment group. Specifically, the MMRM will be fit with CFB in biomarkers up to Week 96 as the dependent variable, and treatment group, categorical visit, visit-by-treatment interaction, baseline (from the Core Study) biomarker, and APOE e4 status of carrier vs. non-carrier as fixed effects.

Input for the models will be non-missing data at all analysis visits up to and including Week 96, as specified in Tables Table 7-12, Table 7-28, Table 7-30, Table 7-32, and Table 7-36. Treatment comparisons will be reported for specified visits as indicated below:

- Plasma biomarkers:
 - AD-pathology (A β 42/40, pTau217): week 12, 24, 48, 72 and 96
 - AD-pathology (MTBR Tau-243 [if available]): week 12, 24, 48, 72 and 96
 - AD-pathology (pTau181 [if available]): week 16, 36, 60 and 84
 - Target engagement (IL1RA): week 1, 2, 4, 6, 8, 12, 24, 36, 48, 72 and 96
 - Neurodegeneration (NfL, GfAP): week 12, 24, 48, 72 and 96
- CSF biomarkers: week 6, 48, 72 and 96
- Amyloid PET parameters: week 48 and 96
- Tau PET parameters: week 48, 72 and 96
- Volumetric MRI parameters: week 48, 72 and 96

Model results, including treatment comparisons will also be obtained as “overall” for the average over all analysis visits in the model.

For Tau PET parameters [Table 7-39], a pMMRM model will be additionally conducted. The integrated PD analyses via MMRM and pMMRM will be based on the subset with redefined core baseline.

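### Averaging every PD biomarker record in a window lets an ARIA-triggered lumbar puncture stand as the Titration Cohort's LTE Week 48 CSF value, and blends widely spaced volumetric MRI scans for AL002 participants who enter the LTE early

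*SAP*

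**What the plan says.** For continuous exploratory PD biomarkers, SAP 7.1.3.2 states that "if multiple valid, non-missing, continuous records exist in a post-baseline analysis visit window, then the average of these records will be taken". Efficacy data (7.1.3.1), continuous safety data and categorical PD data (7.1.3.2) instead use the record nearest the target day. Nothing in the SAP sets unscheduled PD records aside.

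**CSF.** Table 7-31, and footnote b of Table 7-30, give the Titration Cohort a single post-baseline window: LTE Week 48, target Day 337, open to any day after LTE Day 1. SAP 3.1 puts titration at 24 or 32 weeks. Protocol 7.11.2 lets an unscheduled LP be requested after any ARIA event.

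**Volumetric MRI.** SAP 6.5 and Table 7-39 class it as a PD biomarker, so the averaging rule governs. In Table 7-12, Group T-T stays on Core Study Day, with windows [254, 421], [422, 589] and [590, 715] for Weeks 48, 72 and 96. The placebo part of the P-TC column stops at LTE Day 1. SAP 7.7.3 reports comparisons as "Volumetric MRI parameters: week 48, 72 and 96". The AL002 groups contribute "integrated data up to Week 96 since the initiation of study treatment from both the Core Study and the LTE study", and placebo contributes "the data from the Core Study and the LTE screening data for the placebo treatment group". The protocol adds two timing rules: "the MRI should occur at least 5 days prior to the next dose administration and no more than 10 days prior" (Table 9, footnote g) and "Baseline MRIs are required if the last MRI occurred more than 90 days prior to the first dose" (synopsis, study periods).

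**The concern.** Averaging is harmless when a window holds one record, or records close together. It is not harmless when a window is much wider than the spacing of the assessments, because the result then describes a time other than its label.

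In the CSF case the label is plainly wrong: a sample taken part-way through titration, below the target dose, is reported as LTE Week 48, alone or blended.

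In the MRI case the blending depends on arm. The AL002 windows continue through the LTE and can take post-dose scans; the placebo windows cannot. At stake is the timing behind the modelled AL002-versus-placebo volume differences at Weeks 48, 72 and 96. If volume change is steady, a timing gap between arms appears as a difference in change. If volume has reached a plateau, it does not.

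**Working it through.** **The plan's own windows reproduce.** Each Group T-T upper bound is the midpoint of adjacent target days: (337 + 505)/2 = 421; (505 + 673)/2 = 589; (673 + 757)/2 = 715. The later T-T targets equal the LTE target plus 700 (57 + 700 = 757), so the table is laid out for LTE Day 1 on Core Day 701 (Week 100). A participant entering then has one scheduled scan per window and nothing is blended.

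**CSF.** An ARIA-triggered LP averaged with a Day 337 sample has mean day (LP day + 337)/2:
- Day 85: (85 + 337)/2 = 211
- Day 169: (169 + 337)/2 = 253
- Day 225: (225 + 337)/2 = 281

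With no Week 48 sample, the ARIA-triggered LP alone is the LTE Week 48 value. The main estimand's 37-day cut-off runs from study drug discontinuation, so it does not remove an LP taken while dosing is only suspended.

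**MRI, one participant.** Last Core dose on Day 337; LTE Day 1 is 28 ± 5 days later, Core Day 360 to 370. The LTE Week 8 scan is 5 to 10 days before the dose due 56 days after entry, so 46 to 51 days after entry: Core Day 406 to 421. That lies inside [254, 421] and is averaged with the Day 337 scan. The mean is (337 + 406)/2 = 371.5 to (337 + 421)/2 = 379, which is 34.5 to 42 days late, or 10% to 12% of 337.

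**MRI, which entrants.** I placed Core scans at Days 337, 505 and 673 and LTE scans at their target days, 56 days apart from LTE Week 8 to 40. Two or three scans share a window for entry at about Core Weeks 48 to 84. Entry at Week 52 puts Days 477, 533 and 589 in Week 72, a span of 112 days. Among windows with two or more scans, the average falls between 28 days early and 56 days late. Entry at Weeks 88 to 100 gives at most one such scan per window. A required screening MRI can stretch this range. With entry on Core Day 645 (Week 92), the last Core scan is 645 − 505 = 140 days old. A screening scan 10 to 28 days before entry (Days 617 to 635) and the LTE Week 8 scan (Days 691 to 696) then both fall in Week 96.

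**MRI, arm level.** The rollover distribution is not in the documents, so these inputs are assumptions:
- last Core dose equally likely at each of the 13 four-weekly visits from Day 337 to Day 673;
- Core scans at Days 337, 505 and 673 if on or before the last dose (inferred from Table 7-12);
- LTE Day 1 at last dose + 28, shifted by −5 to +5 days;
- LTE scans 5 to 10 days before dosing;
- a screening scan 10 to 28 days before LTE Day 1 when the last Core scan is more than 90 days old;
- linear volume change.

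This gives 6 × 11 × 19 = 1,254 scenarios. For each arm and visit, the shift is the mean of (value day − target day)/target day over participants with data. The gap is the AL002 shift minus the placebo shift. Ranges are the minimum and maximum over scenarios.

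| Visit | AL002 shift, averaging | AL002 shift, closest | Gap, averaging | Gap, closest |
|---|---|---|---|---|
| Week 48 | +0.8% to +1.9% | 0% | +0.8% to +1.0% | 0% |
| Week 72 | +0.7% to +2.6% | −0.4% to +1.2% | +2.7% to +5.0% | +1.6% to +4.0% |
| Week 96 | −4.0% to −2.0% | −1.0% to +1.2% | +0.5% to +3.7% | +3.2% to +6.7% |

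At Week 96 the closest-record gap is the larger in all 1,254 scenarios. The placebo value there comes mostly from early screening scans (shift −6.1% to −3.7%), and averaging also pulls AL002 early, which partly cancels. Only 3 or 4 of the 13 rollover visits supply placebo Week 96 data in this model.

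**The case against.** Averaging is prespecified uniformly for continuous PD biomarkers and reduces noise. The windows are laid out for entry at Week 100, where nothing blends, and the number of early entrants is not stated. The CSF case needs an optional procedure, a discretionary request after ARIA and, for blending, a Week 48 sample in the same person; it reaches only descriptive summaries for the Titration Cohort. All of this stands and limits the weight of the point. It does not rescue the CSF label. Nor is early entry fanciful: parent dosing is for up to 96 weeks (Protocol 1.2.2), Table 7-12 caps placebo windows at LTE Day 1 from Week 48, and LTE data can precede Week 96 only if someone entered early.

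A reader might infer three stronger things.
- **That closest-record selection should replace averaging for MRI.** Looking at AL002 alone this is tempting: its mean absolute distance from target was never larger under closest-record, at any of the three visits, in the 1,254 scenarios or in 66 more without a screening scan. But SAP 7.7.3 reports comparisons with placebo, and on that measure the change makes Week 96 worse.
- **That averaging biases the comparison in a fixed direction.** Individual offsets run from early to late and depend on entry time, and any effect on volume depends on the shape of change.
- **That everyone entering before Core Week 96 is affected.** With Core and on-treatment LTE scans alone, blending stops at about Week 84; a screening scan extends it only for some entry times.

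**Conclusion.** The point holds at the level of something to consider. The CSF part follows from the SAP text and needs no distributional assumption: a mid-titration LP, alone or averaged, is labelled LTE Week 48. How often that would happen is not given.

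The MRI part is a real mechanism of unknown arm-level size. The gaps of +0.8% to +1.0%, +2.7% to +5.0% and +0.5% to +3.7% of the target day at Weeks 48, 72 and 96 rest on evenly spread rollover, linear change, the inferred Core scan days and the required screening MRI. On the same assumptions neither selection rule is better at all three visits, so the documents support a sensitivity analysis, not a change of the main rule. The MRI and CSF endpoints are exploratory; primary, secondary and safety results are untouched.

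**What to change.** **CSF.** Add one sentence to SAP 7.1.3.2: in all treatment groups, ARIA-triggered unscheduled LPs are excluded from scheduled-visit CSF summaries and models and are listed separately. Covering every group avoids an arm-specific rule; the Group T-T CSF windows are also wide (for example Week 96, [590, 855]) and feed the model. The cost is that a participant whose only post-baseline LTE sample is ARIA-triggered drops out of the summary.

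**Volumetric MRI.** Keep averaging as the main rule. Prespecify a sensitivity analysis using the SAP's safety rule (nearest the target day, the later if equidistant, same-day records averaged). Report the actual scan day by arm and visit, so that readers can see the timing gap instead of assuming it. The cost is a little extra programming. Neither change needs new data.
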